1.5.1 Potential Risks

1.5.1.1 Potential Risks of VIS410 Administration

The potential human toxicity of VIS410 should be evaluated in the context of the human experience in clinical studies. As described in Section 1.3, GI AEs, such as transient loose stool/diarrhea and abdominal cramping, were the most commonly observed AEs in the clinical studies. The frequency and severity of these events were greatly mitigated with administration of a pretreatment regimen consisting of an antihistamine and an NSAID.

In mice treated with 4 doses of VIS410 over 14 days, 14 of 384 animals had severe systemic hypersensitivity (anaphylaxis) with death within 1 to 2 hours after the fourth dose. This was not considered to be a VIS410 specific effect as the NOAEL was 250 mg/kg but rather a consequence of immunological response in mice to a human antibody. ADAs were found in 8 animals at the end of the 28-day recovery period; other human antibodies have elicited ADA in mice without clinical problems in humans.

Administration of VIS410, IV once weekly for 4 weeks in cynomolgus monkeys was well tolerated. All animals survived and there were no abnormal clinical observations suggesting distress to the animals (hypersensitivity-related or other) throughout the duration of the study period (including the administration or recovery periods).

ADAs were elicited in 3 of the 42 (7%) samples that had a reduction in titers that were most likely due to drug exposure. As with the mice, there were no findings suggesting VIS410 toxicity in clinical, laboratory, or pathology examinations.

In an in vitro–soluble cytokine release assay performed using human whole blood, VIS410 did not stimulate any dramatic or pervasive release of any pro-inflammatory cytokine (see Section 1.2).

Pharmacological class effects commonly associated with marketed monoclonal antibody products used for treatment in humans include serious infusion reactions including anaphylaxis (see Section 1.3). VIS410 is to be administered as a single infusion and is directed at an exogenous viral target. As a result, it is considered to be of low probability that other SAEs (such as infection risks reported for approved monoclonal antibodies directed against endogenous human protein targets or immune modulating cytokines often administered as multiple doses over a long period) will be observed with VIS410.

As described in Section 1.3, a single administration of VIS410 to healthy volunteers was safe and well tolerated. The potential exists for subjects to experience cramping or loose stools, but pretreatment with histamine antagonists with an NSAID (ibuprofen or acetylsalicylic acid) substantially ameliorated the GI effects.

Given the potential for acute severe hypersensitivity and other adverse reactions observed with other monoclonal antibody therapies, subjects should be closely monitored for relevant signs and

symptoms following administration of VIS410. VIS410 should only be administered when personnel and therapies are immediately available for the treatment of anaphylaxis and other hypersensitivity reactions.

For more detailed information on VIS410, refer to the current Investigator's Brochure.⁸

1.5.1.2 **Potential Risks of Oseltamivir Administration**

Oseltamivir (Tamiflu) is indicated for the treatment of uncomplicated influenza infection in patients who have been symptomatic for no more than 2 days.

Oseltamivir is contraindicated in patients with known hypersensitivity to any of the components of the product.

The following reactions have also been reported following treatment with oseltamivir therapy during clinical studies or post-marketing:

- Body as a whole: Swelling of the face or tongue, allergy, anaphylactic/anaphylactoid reactions
- Dermatologic: Dermatitis, rash, eczema, urticaria, erythema multiforme, Stevens-Johnson syndrome, toxic epidermal necrolysis
- Digestive: Hepatitis, liver function tests abnormal
- Cardiac: Arrhythmia
- Gastrointestinal: Nausea, vomiting, GI bleeding, hemorrhagic colitis
- Neurologic: Seizure
- Metabolic: Aggravation of diabetes
- Psychiatric: Delirium, including symptoms such as altered level of consciousness, confusion, abnormal behavior, delusions, hallucinations, agitation, anxiety, nightmares

For more information, refer to the prescribing information for oseltamivir.⁹

1.5.1.3 **Potential Risks of Diphenhydramine, Ibuprofen, and Acetylsalicylic Acid Administration**

The risk associated with the use of a single over-the-counter dose of diphenhydramine, ibuprofen, and acetylsalicylic acid in this study is considered low.

Many of the adverse reactions due to NSAIDs, such as acetylsalicylic acid or ibuprofen, are dose and duration dependent.

Ibuprofen and acetylsalicylic acid are contraindicated in patients with known hypersensitivity to NSAIDs and acetylsalicylic acid-induced asthma. Ibuprofen is contraindicated for treatment of perioperative pain in the setting of coronary artery bypass graft surgery.

Ibuprofen may cause an increased risk of serious cardiovascular thrombotic events, myocardial infarction, and stroke, which can be fatal. Patients with cardiovascular disease or risk factors for cardiovascular disease may be at greater risk.

NSAIDs cause an increased risk of serious GI AEs, including bleeding, ulceration, and perforation of the stomach or intestines, which can be fatal. Elderly patients are at greater risk for serious GI events.

Long-term administration of NSAIDs has resulted in renal injury. Patients at greatest risk of this reaction are those with impaired renal function, heart failure, liver dysfunction, those taking diuretics and ACE inhibitors, and the elderly. NSAIDs should be avoided in patients with severe renal failure.

NSAIDs can cause serious skin AEs, such as exfoliative dermatitis, Stevens-Johnson syndrome, and toxic epidermal necrolysis.

Acetylsalicylic acid can result in GI side effects, such as stomach pain, heartburn, nausea, vomiting, dyspepsia, and GI bleed. Patients with history of active peptic ulcer disease should avoid acetylsalicylic acid.

The following adverse reactions have been reported following acetylsalicylic acid administration:

- Body as a whole: Fever, hypothermia, thirst
- Cardiovascular: Dysrhythmias, hypotension, tachycardia
- Central nervous system: Agitation, cerebral edema, coma, confusion, dizziness, headache, subdural or intracranial hemorrhage, lethargy, seizures
- Fluid and electrolyte: Dehydration, hyperkalemia, metabolic acidosis, respiratory alkalosis
- Gastrointestinal: Dyspepsia, GI bleeding, ulceration and perforation, nausea, vomiting, transient elevations of hepatic enzymes, hepatitis, Reye syndrome, pancreatitis
- Hematologic: Prolongation of the prothrombin time, disseminated intravascular coagulation, coagulopathy, thrombocytopenia
- Hypersensitivity: Acute anaphylaxis, angioedema, asthma, bronchospasm, laryngeal edema, urticaria
- Musculoskeletal: Rhabdomyolysis
- Metabolism: Hypoglycemia (in children), hyperglycemia
- Reproductive: Prolonged pregnancy and labor, stillbirths, lower birth weight infants, antepartum and postpartum bleeding
- Respiratory: Hyperpnea, pulmonary edema, tachypnea
- Special senses: Hearing loss, tinnitus. Patients with higher frequency hearing loss may have difficulty perceiving tinnitus. In these patients, tinnitus cannot be used as a clinical indicator of salicylism.

- Urogenital: Interstitial nephritis, papillary necrosis, proteinuria, renal insufficiency and failure

For more information, refer to the prescribing information for ibuprofen¹⁰ and acetylsalicylic acid.¹¹

Diphenhydramine is contraindicated in patients with hypersensitivity to diphenhydramine hydrochloride and other antihistamines of similar chemical structure. Antihistamines should be used with caution in patients with narrow-angle glaucoma, stenosing peptic ulcer, pyloroduodenal obstruction, symptomatic prostatic hypertrophy, or bladder-neck obstruction.

Diphenhydramine may cause drowsiness, and patients should be warned about engaging in activities requiring mental alertness, such as driving a car or operating appliances, machinery, etc. Diphenhydramine may diminish mental alertness, and is more likely to cause dizziness, sedation, and hypotension in elderly patients.

Diphenhydramine should be used with caution in patients with a history of bronchial asthma, increased intraocular pressure, hyperthyroidism, cardiovascular disease, or hypertension.

The following reactions have also been reported following treatment with diphenhydramine:

- General: Urticaria, drug rash, anaphylactic shock, photosensitivity, excessive perspiration, chills, and dryness of mouth, nose, and throat
- Cardiovascular: Hypotension, headache, palpitations, tachycardia, extrasystoles
- Hematologic: Hemolytic anemia, thrombocytopenia, agranulocytosis
- Central nervous system: Sedation, sleepiness, dizziness, disturbed coordination, fatigue, confusion, restlessness, excitation, nervousness, tremor, irritability, insomnia, euphoria, paresthesia, blurred vision, diplopia, vertigo, tinnitus, acute labyrinthitis, neuritis, convulsions
- Gastrointestinal: Epigastric distress, anorexia, nausea, vomiting, diarrhea, constipation
- Genitourinary: Urinary frequency, difficult urination, urinary retention, early menses
- Respiratory: Thickening of bronchial secretions, tightness of chest or throat and wheezing, nasal stuffiness

For more information, refer to the prescribing information for diphenhydramine.¹²

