5.2.2 Exclusion Criteria

Subjects meeting any of the following criteria are excluded from participation in this study:

1. Known or suspected intolerance or hypersensitivity to VIS410, oseltamivir, pretreatment medications (diphenhydramine, or to both ibuprofen and acetylsalicylic acid [ASA]), or closely related compounds (eg, other monoclonal antibodies).
2. Subjects who have received VIS410 in the past.
3. Subjects who have a history of receiving monoclonal antibody products within 3 months prior to VIS410/placebo dosing or planned administration of another monoclonal antibody during the study period.
4. Subjects who have taken more than 6 doses of an approved antiviral therapy for influenza within the prior 96 hours (eg, oral oseltamivir, inhaled zanamivir, IV peramivir, or oral ribavirin) between onset of symptoms and VIS410/placebo dosing.
5. Subjects with known co-infection with influenza B or other viral respiratory infections (eg, RSV, parainfluenza viruses, respiratory adenoviruses).
6. Subjects with lung transplant or history of severe chronic lung disease, including cystic fibrosis or any condition requiring home oxygen therapy.
7. Subjects on extracorporeal membrane oxygenation at time of randomization.
8. Subjects with ESRD who are not undergoing hemodialysis.
9. Subjects with active graft-vs-host disease, hematopoietic stem cell transplant within the previous 90 days, or human immunodeficiency virus infection with a CD4 cell count of less than 200 per cubic millimeter.
10. High probability of mortality within 48 hours of randomization as determined by the Investigator.
11. Women who are pregnant, breast-feeding, or considering to become pregnant.
12. Subjects in whom nasopharyngeal swabbing is not possible.
13. Subjects weighing less than 45 kg.
14. Enrollment in any other investigational drug or device study, any disease or vaccine study within 30 days prior to Day 1 or within 5 half-lives of the investigational compound, whichever is longer.
15. Presence of any preexisting illness that, in the opinion of the Investigator, would place the subject at an unreasonably increased risk through participation in this study.
16. Subjects unable to comply with study protocol procedures and study visit schedules for whatever reason.
17. Known or suspected alcohol or drug abuse, that is, abuse of a level that would compromise the safety or cooperation of the subject in the opinion of the Investigator.

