7.4 The Use of Oseltamivir as Standard of Care

All subjects will receive oseltamivir 75 mg BID for 5 days as part of SOC. Treatment with oseltamivir may be extended for up to 5 additional days (up to 20 doses of total therapy) if clinical symptoms warrant further treatment as assessed by the Investigator. Oseltamivir (Tamiflu) will be provided by the Sponsor. Note: based on SOC, subjects may have started oseltamivir therapy prior to randomization.

For patients unable to swallow, oseltamivir capsules can be opened and mixed with liquid for ease of administration.

Dose adjustment is recommended for patients with a serum creatinine clearance of 60 mL/min or less⁹ (see Table 7).

Table 7. Recommended Dosage Modifications for Treatment of Influenza in Adults with Renal Impairment or End-Stage Renal Disease on Dialysis^a

Renal Impairment (Creatinine Clearance)	Recommended Treatment Regimen^b
Mild (> 60-90 mL/minute)	75 mg BID for 5 days
Moderate (> 30-60 mL/minute)	30 mg BID for 5 days
Severe (> 10-30 mL/minute)	30 mg once daily for 5 days
ESRD patients on hemodialysis	30 mg immediately and then 30 mg after every hemodialysis cycle (treatment duration not to exceed 5 days)
ESRD patients on continuous ambulatory peritoneal dialysis ^c (≤ 10 mL/minute)	A single 30-mg dose administered immediately
ESRD patients not on dialysis	Tamiflu is not recommended

ESRD = end-stage renal disease.

^a Creatinine clearance to be calculated using Cockcroft-Gault formula.

^b Capsules or oral suspension can be used for 30-mg dosing.

^c Data derived from studies in continuous ambulatory peritoneal dialysis patients.

For patients with renal insufficiency, refer to prescribing information for administration of oseltamivir.⁹

The dose of oseltamivir (75 mg BID for 5 days) was chosen for this study based on the approved dose in the United States and other regions for the treatment of uncomplicated influenza infection. The dosage regimen of oseltamivir as the SOC in this study serves as a clinically appropriate, ethically acceptable treatment.

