7.5 Pretreatment Regimen

All subjects will be given a pretreatment regimen of PO or IV diphenhydramine 50 mg plus either ibuprofen 400 mg or acetylsalicylic acid 320-325 mg PO or crushed and given through the nasogastric tube approximately 60 minutes before IV infusion of VIS410/placebo.

If the subject has any history of delayed gastric emptying, including premenstruation syndrome or menstruation, the subject may receive premedications 120 minutes prior to IV infusion of VIS410/placebo.

Refer to the Pharmacy Manual for directions on storage, handling, stability data, and preparation and use of diphenhydramine, ibuprofen, and acetylsalicylic acid.

For more information, refer to the prescribing information for ibuprofen¹⁰ and acetylsalicylic acid.¹¹

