8.3.2 Day of Treatment Procedures (Day 1)

On Day 1, eligibility of the subjects will be confirmed and assessments will be performed as described in Table 1.

All results from the screening procedures required to evaluate eligibility must be available prior to randomization on Day 1. Any abnormal assessment at the screening will be assessed according to its clinical relevance, and if found relevant, the subject will not be included in the study.

Once a subject has fulfilled the entry criteria, he/she will be assigned a unique identifier. The site's unblinded pharmacist or properly trained designee will randomize the subject using the IWRS.

On Day 1, all subjects will receive the pretreatment regimen prior to receiving VIS410/placebo.

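### The protocol cautions against NSAIDs in severe renal failure but requires one for every subject, with no renal exemption and no exclusion of hemodialysis or severe impairment short of ESRD

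*Protocol*

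**What the plan says.** **The caution.** Protocol Section 1.5.1.3, on the risks of the pretreatment drugs, says: "NSAIDs should be avoided in patients with severe renal failure." The sentence closes a paragraph that begins with renal injury from long-term NSAID use. The section opens by calling the risk of one over-the-counter dose of each drug low in this study, and adds: "Many of the adverse reactions due to NSAIDs, such as acetylsalicylic acid or ibuprofen, are dose and duration dependent."

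**The requirement.** Section 7.5 says: "All subjects will be given a pretreatment regimen of PO or IV diphenhydramine 50 mg plus either ibuprofen 400 mg or acetylsalicylic acid". Section 8.3.2 repeats it: "On Day 1, all subjects will receive the pretreatment regimen prior to receiving VIS410/placebo." The Synopsis, Sections 4.1 and 10.2, and SAP Section 2.1 describe the same regimen for all subjects.

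**Eligibility.** The only renal criterion in Section 5.2.2 is exclusion 8, which removes "Subjects with ESRD who are not undergoing hemodialysis". The only criterion that names the pretreatment drugs is exclusion 1, which concerns intolerance and hypersensitivity.

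**Renal function at entry.** Serum creatinine is measured locally within 24 hours before randomization (Table 1, footnote 20). Section 6.5.4 requires creatinine clearance before randomization, for oseltamivir dosing.

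**The concern.** One part of the protocol advises against a class of drug in a group of patients. Another part makes a drug of that class compulsory for everyone, and the entry criteria do not keep that group out. A site with an eligible subject on hemodialysis gets no specific instruction from the protocol.

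Two things are at stake. The first is subject safety, in every arm including placebo, because the pretreatment is common to all. The second is consistency. With about 140 planned sites, some could give the NSAID, some could omit it and some could decline to enrol. Omission has a cost on the protocol's own account: Section 1.3.3.1 concludes that adding a prostaglandin inhibitor or NSAID to an antihistamine was needed to reduce gastrointestinal events further. Severe gastrointestinal events requiring intervention count towards the dosing pause in Section 11.4.

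**Working it through.** No arithmetic applies, and the plan gives no figure to reproduce. The check sets the texts side by side and looks in both documents for anything that reconciles them.

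1. **Are both pretreatment options covered by the caution?** Yes. Section 1.5.1.1 says that "pretreatment with histamine antagonists with an NSAID (ibuprofen or acetylsalicylic acid) substantially ameliorated the GI effects", which names both drugs as NSAIDs, and Section 1.5.1.3 does the same. Switching from one option to the other therefore does not avoid the renal caution. A drug-specific caution, such as that on acetylsalicylic acid and peptic ulcer disease, differs in that the other option remains.

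2. **Is there a renal exemption from the pretreatment?** None was found. The stated variations are the choice of NSAID, the route (oral or IV diphenhydramine, or crushed by nasogastric tube) and the timing (120 minutes for delayed gastric emptying). None depends on renal function.

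3. **Who remains eligible?** Under exclusion 8:
   - ESRD without dialysis: excluded.
   - ESRD on peritoneal dialysis: excluded, because not on hemodialysis.
   - ESRD on hemodialysis: not excluded.
   - Severe impairment short of ESRD: not excluded.

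   The last two groups may fall under the caution and still meet the listed renal criterion.

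4. **Does the caution exempt a single dose?** Not in words. The low-risk statement is about study subjects generally and does not mention renal function. The avoidance sentence has no limit on dose or duration. A reader can reconcile them by inference, but the text does not.

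5. **Is the information available in time?** Yes. Creatinine clearance is known before randomization, but the protocol links it only to oseltamivir.

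6. **Does the SAP settle it?** No. SAP Section 8 counts, by treatment group, the subjects who received an NSAID per protocol. That records compliance and creates no exemption. An omission on renal grounds would simply lower the count.

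**The case against.** The strongest reply is that Section 1.5.1.3 should be read as a whole. It summarises label risks, puts the study-specific judgement first (one dose, low risk), and places the renal sentence in a paragraph about long-term use. It also reserves the word contraindicated for other situations, such as hypersensitivity, and uses softer wording here. This has force: it lowers the likely harm and may be what the sponsor meant. It does not remove the conflict, because the avoidance sentence is unqualified and a site cannot tell whether it applies to the study dose.

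The second reply is that investigators can keep such subjects out. Section 5.2 limits the population to subjects without conditions that the Investigator thinks may raise their risk. Exclusion 15 covers preexisting illness that makes participation unreasonably risky. Sections 6.1.3 and 8.3.2 bar a subject whose abnormal screening result is judged relevant. This also stands. A reader might infer that sites are forced either to break Section 7.5 or to act against the risk section. The documents do not support that, since declining to enrol complies with the protocol. But these clauses are discretionary, mention neither renal function nor NSAIDs, and do not say what to do once such a subject is enrolled.

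A reader might also infer from the oseltamivir table (Section 7.4, Table 7) that subjects with severe impairment or on hemodialysis are expected, because it has rows for both. The table does not show that. It also has rows for ESRD on peritoneal dialysis and ESRD without dialysis, both barred by exclusion 8. What can be said is that the criteria do not exclude the two groups.

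**Conclusion.** The inconsistency is real and should be corrected, as a matter of subject safety and consistent pretreatment. Sections 7.5 and 8.3.2, applied as written to subjects whom exclusion 8 leaves eligible, can lead to a drug being given that Section 1.5.1.3 says to avoid.

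Its size cannot be stated. Neither document gives the expected number of subjects with severe impairment or on hemodialysis among the approximately 120 planned, and it may be small. The conclusion assumes that severe renal failure, which is undefined, includes ESRD on hemodialysis. Whether it also covers the severe category in Table 7 (creatinine clearance above 10 and up to 30 mL/minute) is plausible, but the documents do not make that link.

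A reader might go further and infer a bias in the treatment comparison. The documents do not support that: the pretreatment rule is identical in all arms, staff who assess subjects and decide on their care are blinded (Section 10.2), and no endpoint, sample-size figure or error rate depends on this point.

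**What to change.** Reconcile Sections 1.5.1.3, 5.2.2, 7.5 and 8.3.2 so that they give one consistent instruction for subjects on hemodialysis or with severe renal impairment. The text should state whether the caution applies to the single study dose and what severe renal failure means. If renal function bears on the pretreatment, link it to the creatinine clearance already obtained before randomization. The choice of clinical rule belongs to the sponsor's medical team, and this review takes no position on it.

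Carry the result into the Synopsis, Sections 4.1 and 10.2, and SAP Section 2.1. Define NSAID received per protocol in SAP Section 8 to match, so that any omission permitted by the reconciled text is not counted as non-compliance.

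The cost is protocol wording, a short SAP edit and notice to sites. No new assessment is needed, because creatinine clearance is already collected. A change to eligibility or pretreatment would need ethics committee approval under Section 12.3.1.

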1.5.2 Potential Benefits

Animals that received VIS410 as either treatment or prophylaxis experienced prolonged survival compared with vehicle/placebo-treated animals following challenge with various strains of influenza A virus.

At this time, the actual benefits of VIS410 for the treatment of influenza patients are unknown. However, data from a recently conducted Phase 2a human challenge study in 31 healthy

volunteers given influenza A demonstrated a statistically significant reduction in viral AUC following treatment with VIS410 compared with placebo with a shorter duration of symptoms (2 days) in the VIS410-treated group compared with the placebo group.

